## **8 MANAGEMENT OF MISSING DATA**

In the event of incomplete dates, proceed as follows:

- If the year XXXX is known, but not the day or month, 15/06/XXXX will be entered.
- If the month YY and year XXXX are known, but not the day, 15/YY/XXXX will be entered.

For all other variables, no criterion for substituting missing data will be used.

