- IC4: *Treatment with axitinib, as second-line or further line treatment and with progression-free survival PFS of 9 months or more or with disease progression at the first response assessment.*

It must be verified that in "Treatment with axitinib", "Treatment line in which it has been received" is  $\geq 2$ .

It must be verified that the patient meets one of the following two conditions:

- "*Progression-free survival PFS of 9 months or more*": the time from the start of treatment with axitinib to disease progression or death by any cause is  $\geq 9$  months (see definition of PFS in section 7. Definition of variables).

or

- "*Disease progression at the first response assessment*": PD has been indicated in "Treatment with axitinib/ Best response to treatment".

If there is a contradiction between the binary variables and the information shown in the CRF, the latter shall be assumed valid.

A list of candidate patients who are non-evaluable must be made, and after approval or rectification by the study sponsor/coordinator, the list of non-evaluable patients who will be excluded from the analyses will be closed.

The sponsor will be informed of the number of non-evaluable study patients for the analysis and the reasons for non-inclusion, for consultation and confirmation prior to starting the analyses.

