## 7 DEFINITION OF VARIABLES AND OBJECTIVES

In addition, the following variables will be calculated from the CRF data:

NOTE: In patients with dates after the date of the IC visit / signature, the date of the IC visit / signature has been considered as the date of the last check. Due to the retrospective nature of the study, no data can be collected after the patient was included in the IC study / signature.

- Age (years) of patient at time of visit= (Visit date – Date of birth) / 365.25
- Age (years) at first diagnosis= (Date of first diagnosis – Date of birth) / 365.25
- Age (years) at the initiation of axitinib= (start date of axitinib – Date of birth) / 365.25
- Number of metastatic locations = sum (Lymph nodes, CNS, Hepatic, Pulmonary, Bone, Other).
- • Neutrophil / lymphocyte ratio. It will be categorized as follows:  $\leq 3$ ,  $> 3$ . "Before the beginning of the first line" and "At the beginning of treatment with axitinib" will be analyzed. This ratio is not calculated on axitinib suspension because there is no current lymphocyte value data in that part of the CRF.
- Time (months) between first diagnosis and nephrectomy = (Date of nephrectomy – Date of first diagnosis) / 30.4375. A list with the information (site, patient, date of first diagnosis, date of nephrectomy and the calculated time) in cases in which the time is negative (with date of nephrectomy before or equal to date of first diagnosis) will be displayed, and these cases will not be included in the descriptive analysis
- Time (months) between first diagnosis and radiotherapy = (Date of radiotherapy – Date of first diagnosis) / 30.4375. A list with the information (site, patient, date of first diagnosis, date of radiotherapy and the calculated time) in cases in which the time is negative (with date of radiotherapy before or equal to date of first diagnosis) will be displayed, and these cases will not be included in the descriptive analysis.
- Time (months) between first diagnosis and 1st-line treatment = (Date of the initiation of 1st-line treatment – Date of first diagnosis) / 30.4375. A list with the information (site, patient, date of first diagnosis, date of 1st-line treatment and the calculated time) in cases in which the time is negative (with date of 1st-line treatment before or equal to date of first diagnosis) will be displayed, and these cases will not be included in the descriptive analysis

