- Duration (months) of previous 1st-line treatment = (Date of end of 1st-line treatment – Date of start of 1st-line treatment) / 30.4375. If a patient is detected in whom this duration cannot be calculated or a negative time is left, it will not be considered in the descriptive analysis, and a list will be shown with the information related to this calculation of said patient.

- 
- Pre-treatment of 1st line: a descriptive table with the collected drugs will be shown (if necessary, a list will be sent to the sponsor for the grouping of these drugs). In addition, the registered drugs will be grouped into three groups: Sunitinib, Other iTK, and Others, and the descriptive table will be included in the report.
  - Duration (months) of previous 2nd-line treatment =  
 $(\text{Date of end of 2nd-line treatment} - \text{Date of start of 2nd-line treatment}) / 30.4375$ . If a patient is detected in whom this duration cannot be calculated or a negative time is left, it will not be considered in the descriptive analysis, and a list will be shown with the information related to this calculation of said patient.
  - Duration (months) of previous 3rd-line treatment =  
 $(\text{Date of end of 3rd-line treatment} - \text{Date of start of 3rd-line treatment}) / 30.4375$ . If a patient is detected in whom this duration cannot be calculated or a negative time is left, it will not be considered in the descriptive analysis, and a list will be shown with the information related to this calculation of said patient.
  - Duration (months) of previous 4th-line treatment =  
 $(\text{Date of end of 4th-line treatment} - \text{Date of start of 4th-line treatment}) / 30.4375$ . If a patient is detected in whom this duration cannot be calculated or a negative time is left, it will not be considered in the descriptive analysis, and a list will be shown with the information related to this calculation of said patient.
  - Duration (months) of previous 5th-line treatment or further =  $(\text{Date of end of 5th-line treatment} - \text{Date of start of 5th-line treatment}) / 30.4375$ . It will be analyzed only if there is an adequate sample (enough high) of patients with 5th or later previous lines.
  - Duration (months) of treatment with axitinib =  
 $(\text{Date of end of axitinib treatment or of latest follow-up if not suspended} - \text{Date of start of axitinib treatment}) / 30.4375$
  - Time (months) to increase or Time (months) to reduction of axitinib dose =  

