 $(\text{Dose increase date or Dose reduction date} - \text{Start date of treatment with axitinib}) / 30.4375$
  - Duration (months) of subsequent treatments =  
 $(\text{Date of end of subsequent treatment or of latest follow-up if not suspended} - \text{Date of start of subsequent treatment}) / 30.4375$ . In the case of several subsequent treatments per patient, proceed as follows: the duration in months of each of the subsequent treatments will be calculated (from the start date to the end date or last check if it continues). This will be done for all subsequent treatments and then proceed to make the sum per patient of all durations of subsequent treatments

- Progression-Free Survival (PFS, in months) =  
 (Date of Disease Progression on treatment with axitinib or death from any cause – Date of start of treatment with axitinib) / 30.4375  
 If there is no progression or death, the case is censored as  
 PFS (months) = (Date of latest follow-up – Date of start of treatment with axitinib) / 30.4375
- Time to progression (TTP, in months) =  
 (Date of Disease Progression – Date of start of treatment with axitinib) / 30.4375  
 If there is no progression, the case is censored as  
 TTP (months) = (Date of latest follow-up – Date of start of treatment with axitinib) / 30.4375
- Overall Survival (OS, in months) = (Date of death – Date of start of treatment with axitinib) / 30.4375  
 If death has not occurred, the case is censored as  
 Overall Survival (OS, in months) = (Date of latest follow-up – Date of start of treatment with axitinib) / 30.4375
- Overall Survival since the start of first-line treatment (OS, in months) = (Date of death – Date of start of first-line treatment) / 30.4375  
 If death has not occurred, the case is censored as  
 Overall Survival (OS, in months) = (Date of latest follow-up – Start date of first treatment) / 30.4375
- Patient subgroups
  - A-Long-term responders: comprising patients with PFS  $\geq 9$  months.
  - B-Refractory (primary): comprising patients with best response to treatment = PD. This date is collected in the CRF form “axitinib treatment”.
- MSKCC risk group (described in appendix 11.1.). It will be analysed “Before the beginning of the first line”. These calculations will be performed on patients who have data on all the variables involved (in the case of a patient who does not have data on all the variables but has > 2 factors, it will be classified in the “Poor” risk group.

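### Setting year-only dates to 15 June without respecting known date order can move patients across the 9-month PFS cut and produce negative PFS, for which the SAP has no rule

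*SAP*

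**What the plan says.** SAP section 8 has two date rules. For a year-only date: "If the year XXXX is known, but not the day or month, 15/06/XXXX will be entered". For a missing day: "If the month YY and year XXXX are known, but not the day, 15/YY/XXXX will be entered". Neither refers to any other date of the same patient, and no sensitivity analysis is attached.

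These dates feed the following items:

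- **PFS** (SAP section 7): "Date of Disease Progression on treatment with axitinib or death from any cause – Date of start of treatment with axitinib) / 30.4375".
- **Long responders** (section 7): "A-Long-term responders: comprising patients with PFS" of at least 9 months. The check of inclusion criterion 4 in section 2.1 uses the same quantity: "the time from the start of treatment with axitinib to disease progression or death by any cause is" at least 9 months.
- **Refractory patients** (section 7): "B-Refractory (primary): comprising patients with best response to treatment = PD". No date enters this definition.
- **Durations of prior lines 1 to 4** (section 7): negative or non-calculable values are listed and omitted from the descriptive summaries. The wording is: "If a patient is detected in whom this duration cannot be calculated or a negative time is left, it will not be considered".
- **Time from diagnosis to nephrectomy** (section 7): a listing "in cases in which the time is negative (with date of nephrectomy before or equal to date of first diagnosis) will be displayed", and the case is left out. The same holds for radiotherapy and first-line treatment.

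For PFS, time to progression (TTP), overall survival and axitinib duration, section 7 says nothing about negative values. Its opening note takes the visit/consent date as the last check when a date falls after it. That acts on the upper side only.

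**The concern.** The primary comparison is between two groups, and one of them is defined by a time cut at 9 months. A rule that can move that time by several months, in either direction, can take a true long responder out of the study (failing criterion 4) or label a shorter-PFS patient a long responder. It can also place progression before axitinib start. The SAP does not say what the analyst should then do with the negative PFS or TTP.

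A second route runs through the candidate factors. Section 7.1 cuts first-line duration at 3, 6, 9 and 12 months and tests it against group membership. A year-only date can push it into another category or make it negative. Negative values are left out of the descriptive analysis, and these come mainly from short intervals, so the loss is informative.

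**Working it through.** The documents give no misclassification figure, so there is nothing to reproduce. The inputs are:

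- the 15 June rule (SAP section 8) and the divisor 30.4375 (SAP section 7);
- median axitinib PFS of 6.7 months overall, 4.8 after sunitinib and 12.1 after cytokines (Protocol section 6.1.6), for illustration;
- about 60 patients (SAP section 2.1) at about 2:1 (Protocol abstract), so about 40 long responders and 20 refractory.

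**Largest error from one imputed date.** If the true date is 31 December, it is imputed 199 days early: 199 / 30.4375 = 6.5 months. If it is 1 January, it is imputed 165-166 days late: 166 / 30.4375 = 5.5 months. When only the day is missing the error is at most 16 / 30.4375 = 0.5 months, so the month-year rule is not the problem. With both dates year-only the error approaches 12 months.

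**Worked cases, progression date year-only.**

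| Axitinib start | True progression | True PFS | Imputed PFS |
|---|---|---|---|
| 1 Nov 2015 | 20 Nov 2016 | 385 / 30.4375 = 12.6 | 227 / 30.4375 = 7.5 |
| 1 Sep 2015 | 10 Jan 2016 | 131 / 30.4375 = 4.3 | 288 / 30.4375 = 9.5 |
| 1 Sep 2015 | 20 Nov 2015 | 80 / 30.4375 = 2.6 | -78 / 30.4375 = -2.6 |

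The first loses a true long responder, the second creates a false one, and the third puts progression before start.

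**How often, per affected patient.** This is a simulation of 1,000,000 patients, with axitinib starts uniform over 2013-2016 and exponential PFS at each of the three medians. The uniform starts and the exponential shape are assumptions; the documents do not give them.

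Only the progression date year-only:

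- 9-19% of true long responders fall below 9 months (19% at median 4.8, 15% at 6.7, 9% at 12.1).
- 17-19% of patients with true PFS between 3 and 9 months rise to 9 or more.
- 42-43% of patients with true PFS of 3 months or less get a negative PFS; over all such patients the figure is 9-19%.

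Only the start date year-only: 6-14% of true long responders fall below 9 months.

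Both dates year-only: PFS is exactly 0 or close to a multiple of 12 months, never negative. It is exactly 0 for 28-53% of an unselected population. At the planned 2:1 mix the share is about 32%: 4-5% of long responders and 88% of patients with PFS of 3 months or less, so (2 x 4.5 + 88) / 3 = 32.

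**Which intervals turn negative.** At medians 4.8 and 6.7, 76-78% of the negative intervals have a true length of 3 months or less, and none is longer than about 6.6 months. The same date arithmetic applies to prior-line durations, although their true distribution is not known here.

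**Does bounding alone cure it?** No. Replacing 15 June by the midpoint of the feasible window removes the impossible orderings but still leaves 8-17% of long responders below 9 months. In the second worked case the window for progression runs from 1 January to 31 December 2016, so PFS lies between 122 / 30.4375 = 4.0 and 487 / 30.4375 = 16.0 months. The data cannot settle the group.

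**The case against.** Several points count against a strong reading, and most of them stand.

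- **Frequency.** The documents do not say how many dates are year-only. SAP section 2.1 requires the axitinib start date to be present, and the CRF asks for a progression date. An unknown-date option is listed only for nephrectomy and radiotherapy. Partial dates may therefore be commoner in remote history than in the dates that drive PFS. Against that, this is a retrospective chart study in which many patients will have died (Protocol section 9.1), and the SAP itself provides for year-only dates.
- **Review.** Exclusions under criterion 4 go on a list that the sponsor or coordinator approves or corrects, and a false long responder must first have been enrolled by the site as eligible. Loss or entry is therefore not automatic. But the SAP gives the review no criterion for imputed dates, and it lets CRF information override the yes/no eligibility entry.
- **Refractory patients.** A reader might infer that they leave their group or turn into long responders, or that a 3-month cut is at risk. SAP sections 5.2 and 7 define them by best response, and the 3-month figure is only an estimate attached to that definition. What remains is an overlap: a patient with PD as best response and imputed PFS of 9 months or more meets both definitions, with no tie-break. Section 7.1 adds some doubt by saying that classification rests on PFS, although it points back to section 5.2.
- **Discarding.** A reader might infer that negative PFS values are dropped. The drop rules cover only pre-axitinib intervals, concern the descriptive analysis, and come with a patient listing, so that loss is visible.
- **Bounds.** The visit/consent cap is a partial upper bound, so it would be wrong to say there is none.

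**Conclusion.** The point holds in limited form. As written, the year-only rule ignores known date order, can carry PFS across the 9-month cut in both directions, and can give a negative PFS or TTP that the SAP does not handle. The group at risk is the long responders; refractory membership does not change. Pre-axitinib intervals, including first-line duration, are exposed separately.

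The size per affected patient is up to about 6.5 months from one imputed date. For a year-only progression date, 9-19% of true long responders are lost, under uniform starts and exponential PFS with medians of 4.8 to 12.1 months. The study-level size cannot be given. If, purely as an assumption, 10 of the 40 expected long responders had a year-only progression date, one or two would be expected to fall below the cut (10 x 0.09 = 0.9 to 10 x 0.19 = 1.9). If none had, the effect on the primary comparison from this source would be nil. The rule should be changed, but the documents do not show that the primary comparison is in fact compromised.

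**What to change.** In SAP section 8:

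1. Constrain every imputed date to the window set by the patient's known preceding and following dates (for progression: not before axitinib start; not after death, last follow-up or consent).
2. Report how many axitinib start, progression and first-line dates were imputed, separately for year-only and month-year.
3. For each patient with a year-only axitinib start or progression date, compute PFS at the earliest and latest feasible dates. Where the two disagree on the 9-month cut, repeat the primary comparison with that patient excluded and then reclassified, as a sensitivity analysis.
4. Do the same for the first-line duration cut-points.
5. State which group takes a patient who meets both definitions.

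Step 1 removes negative intervals caused by imputation; step 3 is what protects the primary comparison. The cost is a short rule and a little code, and a few patients may be left with an openly ambiguous classification. If step 2 shows no year-only key dates, steps 3 and 4 fall away.

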## **9 STATISTICAL METHODOLOGY AND STATISTICAL ANALYSIS**

### **9.1 STATISTICAL METHODOLOGY**

#### **Descriptive analysis:**

Continuous numerical variables will be described using the principal measurements of centralisation and dispersion (mean, median, standard deviation, minimum Min., maximum Max., 25th percentile [Q1], 75th percentile [Q3], N)." 95% confidence intervals shall be given for the main quantitative variables for results associated with the primary objective and the main secondary variables.

There will be two percentage columns in the descriptive analysis of the qualitative variables: the total (%) and valid (% valid) percentages, that is, the percentage of the sum of valid responses plus missing values and the percentage of the total valid responses.

For questions with more than one response option (multi-response questions), multiple response tables will be displayed. These tables will show two percentage columns:

**Inferential analysis:**

When an inferential analysis is required, parametric tests will be used for continuous variables, and non-parametric tests will be used for ordinal, categorical or non-parametric variables. The hypothesis tests to be carried out will be two-tailed test in all cases with a significance level of 0.05. For variables that are not adjusted to a normal (or parametric) distribution, the Mann–Whitney U test (for unpaired data) or the Wilcoxon signed-rank test (for paired data) will be used. The Chi-squared test (or Fisher’s exact test when applicable) shall be used for analysing the contingency tables and for the comparison of proportions and/or frequency distributions.

Survival analyses shall be performed using the Kaplan-Meier method, providing the median, mean, 95% confidence intervals, as well as number of events and number of censored cases.

When it is necessary to compare survival functions, the log-rank test will be used.

The assumptions of normality and homoscedasticity of the variables for the use of parametric tests will be studied.

The level of significance in all the statistical inference tests will be  $\alpha=0.05$ , two-tailed.

Adjustment by multiple comparisons is not planned.

Estimates will be calculated with a 95% confidence level, the SPSS statistical analysis software package, V18.0 or later, will be used.

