## **SCHEDULE**

The administrative procedures of the study are expected to begin with the central IEC and the AEMPS in September/October 2017, with the first sites expected to open in the first quarter of 2018.

Patient recruitment will be carried out competitively for a maximum period of three months following the opening of the last participating study site. No follow-up of patients will be carried out after their inclusion in the study.

Regarding the observation period—given that it is an observational, retrospective study—this will always be prior to the inclusion of the patient in the study, with this starting at the time of diagnosis of the study condition (renal cell carcinoma) and ending at the time of inclusion in the study, or the death of the patient if this occurs first.

The study is expected to end when the data of all enrolled patients have been collected and analysed, which is estimated for 2019.

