## 9.2 STATISTICAL ANALYSES

### Primary objective

A descriptive analysis will be performed of the baseline clinical characteristics (clinical history of renal cell carcinoma, first-line treatment, other treatments prior to axitinib) of the population of patients who are long-term responders with axitinib, in those patients refractories to treatment, and overall.

The baseline clinical characteristics will be statistically compared according to membership to each one of the two extreme treatment response groups.

Efficacy variables will be analyzed and compared between groups of long responders and refractory patients: PFS, time to progression, overall survival, overall survival from the beginning of the 1st line. These analyzes will be added in the statistical report in the sections in which these same analyzes are shown for the total N of patients.

In addition, the association of clinical factors of interest with the benefit of treatment will be analysed by logistic regression (see point 7.1. Primary objective).

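### The SAP asks for a Kaplan-Meier mean of PFS, TTP and OS without a truncation time, so where the longest time is censored the mean is too low and need not be comparable between groups

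*SAP*

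**What the plan says.** SAP section 9.1 (Inferential analysis) sets the summary for every time-to-event endpoint: "Survival analyses shall be performed using the Kaplan-Meier method, providing the median, mean, 95% confidence intervals", with the numbers of events and censored cases. It names the log-rank test for comparing curves. It states no truncation time and does not call the mean restricted.

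SAP section 7 censors each endpoint at the date of latest follow-up. For PFS: "If there is no progression or death, the case is censored as". For TTP: "If there is no progression, the case is censored as". For OS, from axitinib start and from first-line start: "If death has not occurred, the case is censored as".

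The Protocol's Schedule has observation "ending at the time of inclusion in the study, or the death of the patient if this occurs first", and adds: "No follow-up of patients will be carried out after their inclusion in the study". Neither document sets a minimum or common length of follow-up, so a living patient's follow-up depends on when axitinib was started.

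SAP section 9.2 (Primary objective) then says: "Efficacy variables will be analyzed and compared between groups of long responders and refractory patients: PFS, time to progression, overall survival", and OS from first line. SAP section 7.2 repeats PFS, TTP or OS by axitinib line, response group, treatment sequence and a subpopulation of special interest, and OS by subsequent treatment.

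**The concern.** The Kaplan-Meier mean is the area under the curve. If the longest time in a group is an event, the curve reaches zero and the area is complete. If it is censored, the area stops there, unless some rule closes the tail, and the SAP states none. Each group's mean then has its own horizon, set by whichever patient has the longest time. With about 60 patients (Protocol 8.5) at roughly 2:1 (Protocol, Study population), many of the section 7.2 subgroups will be small.

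Means printed side by side would be read as average survival times. They would be too low where patients remain event-free, and part of any difference could reflect follow-up alone. The secondary analyses are descriptive, so the printed estimates are the result there. Where a median is not reached, the mean is the figure a reader falls back on.

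**Working it through.** The plan has no figure of its own to reproduce: it gives no follow-up lengths and says a sample size calculation does not apply.

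**Inputs from the documents**
- OS median 20.1 months and PFS median 6.7 months, both for axitinib in the pivotal trial (Protocol 6.1.6).
- About 60 patients at about 2:1, taken as 40 and 20.

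**Assumptions**
- Exponential survival.
- Censoring uniform over the follow-up ranges shown.

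**Closed form for OS.** True mean θ = 20.1 / ln 2 = 29.0 months. The mean restricted to horizon τ is θ(1 − exp(−τ/θ)):
- τ = 24: 16.3 months
- τ = 36: 20.6 months
- τ = 60: 25.3 months

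**Simulation for OS.** Both groups have the same true survival, and the mean is the area to each group's largest observed time.

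| Follow-up, n = 40 (months) | Follow-up, n = 20 (months) | Average KM means | False gap |
|---|---|---|---|
| 24-60 | 24-60 | 24.8 v 24.6 | 0.2 |
| 9-60 | 3-60 | 24.6 v 24.0 | 0.6 |
| 24-60 | 12-36 | 24.8 v 19.8 | 5.0 |
| 12-66 | 3-30 | 25.3 v 17.8 | 7.5 |
| 24-60 | 6-24 | 24.7 v 15.6 | 9.1 |

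All the means lie below 29.0. The gap is small when the upper limit of follow-up is shared and grows as the upper limits separate. Log-rank rejection was about 5% in the unequal scenarios where it was computed, so the test is not disturbed.

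**Coverage.** With follow-up of 3-60, 9-60, 12-66 or 24-60 months, the average mean is 24.0 to 25.3 and the nominal 95% CI contains 29.0 in about 64-73% of runs. In the 3-30 month group it does so in 2% or fewer.

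**PFS, all patients.** True mean 6.7 / ln 2 = 9.7 months. Follow-up of 24-60 v 6-24 months gives 9.5 v 8.5, a gap of 1.0.

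**PFS, long responders.** Given PFS of at least 9 months, the true mean is 9 + 9.7 = 18.7 months. The restricted mean is 14.9 at τ = 18, 16.6 at τ = 24 and 18.1 at τ = 36.

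**PFS and TTP, refractory patients.** SAP sections 5.2 and 7 define them by progression as best response. Each therefore has an event and nothing is cut off; with no censoring, the Kaplan-Meier mean equals the sample mean.

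**The case against.** The strongest objection concerns size. A reader might infer that follow-up is known to differ between long responders and refractory patients, or between axitinib lines, and that a false gap of 7.5 months should be expected. The documents do not support this. One closing rule applies to everyone, and all groups come from the same sites and recruitment period. The one built-in difference is that long responders need at least 9 months. The mean depends on the longest time, and an early-treated refractory patient may be followed as long as any responder. With a shared upper limit the gap falls to 0.6 months. This part of the objection stands.

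Three further points also stand in part:
- Protocol 9.1 expects many patients to have died before inclusion, so OS censoring may be lighter than simulated. It gives no number, and the inclusion criteria provide for living patients.
- Identical survival is not a realistic null for long responders v refractory patients, who are selected on PFS. The simulation only isolates the part of a difference due to follow-up.
- The same SAP sentence also supplies the median and the event and censoring counts, and no test or regression model uses the mean.

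None of this defines the mean or removes its downward bias and under-coverage. Those occur even with equal follow-up, whenever the longest time is censored.

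**Conclusion.** The concern holds as a weakness in reported estimates, not as an error in a test. Without a horizon, the means for OS and for long-responder PFS and TTP will be too low whenever the longest time is censored. In the assumed OS scenarios with follow-up reaching 60 months or more, the average shortfall is about 4 to 5 months against a true mean of 29.0, with CI coverage of about 64-73%.

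Comparability fails only if maximum follow-up differs between the groups shown, which the documents neither establish nor exclude. The false OS gap runs from about 0.6 months through 5 to 7.5 under the three main contrasts, and reaches 9.1 in the harshest one tried. All these figures rest on exponential survival and assumed follow-up. Unselected PFS is affected by about 1 month at most in the case tried, and refractory PFS and TTP essentially not at all.

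A reader might also infer that the intervals never contain the true mean. That is too strong: they under-cover, and miss almost always only when follow-up is short.

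**What to change.** In SAP section 9.1, do one of the following:
- Delete the mean and report the median with its 95% CI, keeping the event and censoring counts.
- Report a restricted mean, labelled as such, to one stated horizon common to all groups in the table and no later than the smallest of the groups' longest follow-up times.

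Survival at fixed times with 95% CIs is an optional addition that would help where a median is not reached.

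The cost is one sentence in the SAP and a table-shell change, with no new data. A restricted mean to a common horizon discards some late follow-up in the longer-followed groups.
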